Aim 2 examines the changes in biomarkers levels measured over three time points (Baseline, no later than 30 minutes after the end of the first RBC transfusion, 6 hours (+ / - 30 minutes) from the end of first study RBC transfusion, and 18 hours (+ / - 30 minutes) from the end of first study RBC transfusion. Mixed models will be fit to model the linear trajectory of these biomarkers. A model with a random slope and intercept will be considered initially, and the primary parameter of interest will be the treatment group by time interaction. For this analysis, a “modified” intention to treat (ITT) principle will be considered. Only patients randomized to RBC washing who receive at least one unit of the washed cells will be included from RBC washing group in the analysis. Those not receiving RBC washed cells will be in the considered the control group. The reason for this is this aim is focused on mechanistic action and demonstrating biologic plausibility prior to formal evaluation of clinical outcomes (which would be analyzed using traditional ITT considerations). Since the functional form of the changes in biomarkers over time is not known, a discrete (2 D.F. test) representation of time will also be used to gauge the linearity assumption as well as provide a sensitivity analysis to the primary regression model. Standard mixed modeling practices will be utilized (e.g., assessment of residuals, verification of variance components, nested modeling to simply variance components and covariance patterns, etc). This modeling scenario will be conducted for each biomarker of interest. Since prior research have noted that these outcomes are “clustered”, the methodology by Shi et al. will be used to adjust for multiple comparisons.¹⁰⁴ We will also compute O’Brien’s nonparametric global test statistic to provide an overall measure of treatment effect between the two treatment groups.

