The effects of storage duration will also be assessed. The mean age of the transfused blood products will be determined. This value will be used to test for effect modification (interaction with treatment). Specifically, the main effect of RBC age, its interaction action with treatment, time and the treatment-by-time interaction term will be used to determine if the biomarker trajectories are affected by RBC age. It is hypothesized that the washing protocol will attenuate the effects of age resulting in more uniform trajectories over the range of RBC age where as the unwashed RBC will show increases in biomarker values as RBC age increases.

Sample Size Considerations: The sample size for this clinical trial is based on the mechanistic outcomes detailed for Specific Aim 2a. Table 2 in Fremont et al. was used to provide estimates of the range of effect sizes for the biomarkers considered in this study.⁸⁰ Using an approximation of the standard deviation from the interquartile range ($SD \approx IRQ/1.35$), the median effect size was found to be 0.4. This magnitude of change would be relevant, and appropriate to power this study on. With equal allocation between the groups, the sample size for this study is estimated to be $n=78/group$ ($\alpha=0.10$, two-sided; see additional statistical considerations below). Actual power is expected to be higher on account of the repeated measures design. To allow for drop out and “non-feasible” cases, we plan to enroll and randomize patients until 154 patients have undergone surgery and had at least one transfusion on the operative day. We anticipate this may require randomizing up to 190 total patients. Any patients randomized and awaiting surgery when the 154th patient is achieved will also be included. The final sample size may be adjusted further based on the feasibility findings observed in the two-stage design.

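### The claim that repeated measures will raise power above the 78-per-group calculation is unsupported for the linear group-by-time slope that Aim 2a makes primary

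*Combined protocol and SAP*

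**What the plan says.** In the combined protocol and SAP, the Aim 2 paragraph of Statistical Considerations sets the model and the target. On the model it says "Mixed models will be fit to model the linear trajectory of these biomarkers", starting from random intercepts and slopes. On the target it says that "the primary parameter of interest will be the treatment group by time interaction". The same paragraph admits uncertainty about shape ("Since the functional form of the changes in biomarkers over time is not known") and adds a second model: "a discrete (2 D.F. test) representation of time will also be used to gauge the linearity assumption". That second model also serves as a sensitivity analysis. A correction for correlated endpoints and O'Brien's global test are planned as well.

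The paragraph opens "Aim 2 examines the changes in biomarkers levels measured over three time points" but then lists four: baseline, within 30 minutes after the first unit, and 6 and 18 hours after it. Outcome Measures (Specific Aim 2) and Specimen Handling also give four.

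Sample Size Considerations bases the trial on Aim 2a with a standardised effect of 0.4, two-sided alpha of 0.10 and equal allocation, giving 78 per group. It states no power for this calculation; a figure above 80% appears only for the paired Aim 1c test. It then says "Actual power is expected to be higher on account of the repeated measures design". Enrolment stops once 154 patients have been transfused on the operative day, which is 77 per arm.

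**The concern.** Repeated measures do not raise power for every contrast. They help when the contrast uses the draws in which the groups differ and when within-patient correlation removes noise. A linear slope over unequally spaced draws rewards an effect that keeps growing until the last draw. It discounts one that is already present at the first post-transfusion draw or that has faded by 18 hours. The Aim 2a hypothesis is about lower concentrations after transfusion, which does not say which of these patterns to expect.

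The size of the trial rests on this aim. If the sentence is taken at face value, a null slope may be read as absence of a 0.4 SD effect when the test had little chance of finding one of that shape.

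**Working it through.** **1. The plan's own figure.** Two independent means, d = 0.4, two-sided alpha 0.10, power 0.80 (inferred):

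n = 2(1.645 + 0.842)² / 0.4² = 77.3 per group by the normal formula and 77.96 by the t distribution, so 78. One-sided 0.10 at 80% gives 57, two-sided 0.10 at 90% gives 108, and two-sided 0.05 at 80% gives 99. Only the first combination matches, and it contains no repeated-measures term.

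**2. Inputs for the slope.** From the plan: 77 per arm, alpha 0.10 two-sided, four draws, 0.4 SD. Assumed, because the plan gives none of them: draws at 0, 1, 6.5 and 18.5 h (1 h from baseline to draw 2), SD 1 at each draw, equal correlation rho of 0.3, 0.5 or 0.7 between draws, no baseline difference, and the effect shapes below. Alpha is not adjusted for the planned multiplicity correction.

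**3. Formula.** With balanced data the slope estimate is a weighted sum of the four draws. The mean time is 6.5 h, the deviations are −6.5, −5.5, 0 and 12, and the weights relative to the last draw are w = (−0.54, −0.46, 0.00, 1.00). Draw 2 counts almost as a second baseline and the 6 h draw counts for nothing. Because the weights sum to zero, w'Vw = (1 − rho) w'w, with w'w = 1.5035. For group differences δ:

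ncp = |w'δ| / √[(2/77)(1 − rho) × 1.5035]; power = Φ(ncp − 1.645) + Φ(−ncp − 1.645).

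**4. Worked cases, rho = 0.5.** The standard error is √[(2/77) × 0.752] = 0.140.
- Sustained 0.4 SD at all three later draws: w'δ = 0.4 × 0.542 = 0.217, ncp = 1.55, power 0.46.
- Linear growth to 0.4 SD: w'δ = 0.390, ncp = 2.79, power 0.87.
- Sustained, time coded 0, 1, 2, 3: weights (−1, −1/3, 1/3, 1), w'w = 2.222, w'δ = 0.4, standard error 0.170, ncp = 2.35, power 0.76.

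**5. Results at rho 0.3 / 0.5 / 0.7.** Effects in SD at draw 2, 6 h and 18 h. The last column is the discrete-time interaction test with 3 degrees of freedom (noncentral chi-square on the three changes from baseline, critical value 6.25).

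| Shape | Slope, hours | Slope, draw order | Discrete, 3 d.f. |
|---|---|---|---|
| Linear growth to 0.4 | 0.76 / 0.87 / 0.97 | 0.71 / 0.83 / 0.96 | 0.61 / 0.75 / 0.93 |
| (0, 0.4, 0.4) | 0.78 / 0.89 / 0.98 | 0.84 / 0.93 / 0.99 | 0.80 / 0.91 / 0.99 |
| Sustained (0.4, 0.4, 0.4) | 0.37 / 0.46 / 0.64 | 0.64 / 0.76 / 0.92 | 0.68 / 0.82 / 0.96 |
| 6 h peak (0.2, 0.4, 0.2) | 0.17 / 0.20 / 0.26 | 0.38 / 0.47 / 0.65 | 0.52 / 0.65 / 0.86 |
| Gone by 18 h (0.4, 0.4, 0) | wrong sign | zero slope | 0.80 / 0.91 / 0.99 |

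In hours, slope power reaches 0.80 at rho 0.37 for linear growth, 0.81 for the sustained effect and 0.95 for the 6 h peak.

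**6. Random slope.** The plan starts from a model with one. Adding an assumed SD of 0.5 for the change by the last draw, V gains (0.5/18.5)² tt'. Slope power falls to 0.69 / 0.78 / 0.90 for linear growth and 0.32 / 0.39 / 0.49 for the sustained effect.

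**7. Stability.** Varying the baseline-to-draw-2 gap from 0.5 to 4 h moves the sustained case at rho 0.5 between 0.44 and 0.60. Simulation of that case with the 1 h gap (20,000 trials) gave 0.455 for the slope and 0.816 for the 3 d.f. test, against 0.463 and 0.819 by formula.

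**8. Degrees of freedom.** Four draws give three changes from baseline, so a discrete treatment-by-time test has 3. Taking out the linear component leaves 2 for departure from linearity.

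**The case against.** The sentence on power is hedged, and for some analyses it is right. A baseline-adjusted comparison at one post-transfusion draw has residual SD √(1 − rho²), which at 78 per group gives 83.5% power at rho 0.3 and 89.2% at 0.5. It is also right for a linearly growing effect once rho passes about 0.37 without a random slope. So it is unsupported rather than false.

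A reader might infer that the trial is underpowered. The documents do not show that: correlation, shape and time scale are all missing, and the unfavourable shapes are assumptions. The sustained shape needs the full effect within 30 minutes of the first unit, whereas patients are selected for a predicted need of at least four units and the intervention covers every unit on the day of surgery. A build-up is plausible. If the remainder grows linearly, the slope is the better test while less than about 0.60 / 0.58 / 0.54 of the 18 h effect (rho 0.3 / 0.5 / 0.7) is present at draw 2. A plateau by 6 h reverses this: for (0.2, 0.4, 0.4) the slope has 0.59 / 0.71 / 0.89 against 0.65 / 0.79 / 0.94 for the 3 d.f. test.

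A reader might also infer that the discrete-time test must become primary. That does not follow. Under linear growth it loses about 15 / 12 / 5 points, or 16 / 15 / 11 with the assumed random slope. It has no direction, although the hypothesis does. The discrete model and O'Brien's test are already planned, so the aim does not rest on an unchecked straight line.

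Nor is 2 d.f. shown to be an error: the text ties it to checking linearity, where 2 is correct for four draws. Only the count of three time points is a plain slip.

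What survives is the mismatch between the sample-size calculation and the stated primary parameter.

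**Conclusion.** The point holds as a gap in justification. The 78 per group is correct arithmetic for two means and says nothing about a slope. For the slope, the claim of higher power is true for some assumed patterns and false for others: at rho 0.3 to 0.7 with time in hours, power is 0.17 to 0.26 for a 6 h peak and 0.37 to 0.64 for a sustained effect, against 0.76 to 0.97 for linear growth. The unstated time scale alone moves the sustained case at rho 0.5 from 0.46 to 0.76.

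These figures compare contrasts at an unadjusted alpha of 0.10 and are not estimates of the trial's actual power, which the multiplicity correction would lower. The missing inputs and the miscounted draws need no assumption. The matter should be fixed, but it invalidates neither the design nor the planned model.

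**What to change.** 1. In Sample Size Considerations, delete the sentence on higher power, or replace it with power for the chosen primary parameter under a stated effect shape, within-patient correlation, random-slope SD, time scale and multiplicity-adjusted alpha.
2. In the Aim 2 paragraph, state whether time is in hours or draw order.
3. In the same paragraph, change three time points to four, and say that 2 d.f. is the departure-from-linearity test while the discrete treatment-by-time test has 3.
4. Keep the discrete-time model and report the between-group difference with a confidence interval at each draw beside the slope, so that a null slope is not read as no effect.

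This changes wording and reporting only; draws, assays and sample size stay as they are. Making the 3 d.f. test primary is an option for the sponsor to weigh, at a cost of about 5 to 16 points of power if the effect is linear. Adjustment for centre and a common-baseline model are separate questions and do not follow from this point.

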Specific Aim 2: The outcomes measures for aim 2a will be the change in concentration of multiple, validated lung injury biomarkers representing the primary pathways leading to development of lung injury (Table 5). Patients will have blood drawn as soon as possible after the decision to transfuse, as soon as possible after transfusion, but not later than 30 minutes after the end of first study RBC transfusion, 6 hours (+ / - 30 minutes) from the end of first study RBC transfusion, and 18 hours (+ / - 30 minutes) from the end of first study RBC transfusion.

Table 5. Lung injury biomarkers and exploratory potentially pathogenic biologic response modifiers for specific aim 2.

Validated lung injury biomarkers (Aim 2a)	Primary process evaluated	Supporting Reference
Interleukin-6	Inflammation	77-79
Interleukin-8		77-81
Von Willebrand Factor	Endothelial activation/injury	77,80-8570,73-76
Intercellular Adhesion Molecule-1		77,80,86-89
Receptor of Advanced glycation end-products	Epithelial Injury	80,93
Surfactant Protein-D		77,80,90,91
Plasma activator inhibitor-1	Dysregulated coagulation	79,86,94-96
Exploratory biomarkers (Aim 2c)	Primary process evaluated	Supporting Reference
Neutral lipids	Lung inflammation	6,12
sCD40L		3
CCL5/RANTES		13,29,30
RBC-derived microparticles	NO scavenging	16-18
Free Hemoglobin		18-20
N-terminal Brain Natriuretic Peptide	Ventricular stretch/volume-overload	97-99

In addition to these biomarker analyses, we will proceed with detailed assessment of the cardiopulmonary responses to study RBC transfusions administered in the operating room (**Aim 2b**). Specific variables to be assessed and recorded are listed in Table 6. Systemic vascular resistance will be calculated at each time point using the following equation: $SVR \text{ (dyns/cm}^5\text{)} = [(MAP - RAP)/CO] \times 80$. Each of these variables will be assessed and recorded immediately prior to the intervention RBC transfusion and again immediately after the RBC transfusion. Standard operating procedures for these cardiopulmonary assessments will be defined prior to study onset according to previously established recommendations.¹⁰⁰ These secondary outcomes will allow a more detailed assessment of the cardiopulmonary response to RBC transfusion and will be expected to provide important insight into the pathophysiology of TACO. Of note, pulmonary artery catheter placement is standard of care for this patient population at both of the enrolling institutions.

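### The primary Aim 2a model does not adjust for the pre-transfusion biomarker, so its treatment-by-time test keeps baseline sampling error that could be removed at almost no cost

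*Combined protocol and SAP*

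**What the plan says.** Sample Size Considerations: "The sample size for this clinical trial is based on the mechanistic outcomes detailed for Specific Aim 2a". The effect size comes from a published biomarker study in trauma patients: "Using an approximation of the standard deviation from the interquartile range", "the median effect size was found to be 0.4". At two-sided alpha 0.10 and 1:1 allocation this gives 78 per group. The section then adds: "Actual power is expected to be higher on account of the repeated measures design". No correlation and no calculation accompany that sentence.

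Outcome Measures, Specific Aim 2, defines the Aim 2a outcome as a change in biomarker concentration. On the first sample it says: "Patients will have blood drawn as soon as possible after the decision to transfuse". Further draws follow within 30 minutes of the end of the first study transfusion, and at 6 and 18 hours after it.

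Statistical Considerations, Aim 2 paragraph, announces three time points but lists four draws, with baseline among them. It starts from a mixed model with a random intercept and slope, and states that "the primary parameter of interest will be the treatment group by time interaction". A discrete-time version with a 2 d.f. test is the sensitivity analysis. Patients randomized to washing who receive no washed cells are counted as controls.

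Neither this paragraph, Sample Size Considerations nor Additional statistical considerations names the baseline biomarker as a covariate or holds the groups to one baseline mean. The section on predictor variables lists baseline characteristics but does not enter them in this model.

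**The concern.** If baseline is a response and each group has its own intercept, the treatment-by-time term is in effect a comparison of change from baseline. The random intercept absorbs stable differences between patients. The within-patient noise in the baseline draw remains, and it enters the estimated slope difference.

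Every patient is due to give that baseline sample anyway, so conditioning on it, or using randomization to equate the group means at baseline, gives a more precise estimate without more blood or more patients. Precision for these biomarkers is what the sample size is meant to secure. The plan also relies on repeated measures to raise power above the calculated level, and whether they do depends on a correlation that it never states.

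**Working it through.** **1. The plan's figure.** Inputs from Sample Size Considerations: 0.4 SD, two-sided alpha 0.10, 1:1. Power is not stated for Aim 2a; 80% is assumed. A two-sample t-test with 78 per group has 80.0% power, so the 78 reproduces. It is a plain comparison of two means on a cross-sectional SD and uses neither the baseline value nor the interaction. The target of 154 transfused patients is 77 per arm (79.6%), which I use below.

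**2. One post-transfusion draw against baseline.** With unit SD and correlation rho, the variance is 2(1 − rho) for change and 1 − rho² with adjustment. The ratio is (1 + rho)/2: 0.65, 0.75 and 0.85 at rho 0.3, 0.5 and 0.7. Power uses d = 0.4/√variance with 77 per arm.

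| rho | change | adjusted | gain (points) |
|---|---|---|---|
| 0.3 | 67.1% | 82.8% | 16 |
| 0.5 | 79.6% | 88.7% | 9 |
| 0.7 | 93.9% | 96.5% | 3 |

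This is not the planned primary test, and it is not the joint 2 d.f. test either.

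**3. The planned linear slope.** Assumptions: draws at 0, 1, 7 and 19 h (the first post-transfusion draw taken as 1 h after baseline); time rescaled so that the last draw is 1; baseline variance 1, split into intercept variance rho and residual variance 1 − rho; random-slope SD τ over 19 h, in baseline SD units and uncorrelated with the intercept; effect 0.4 SD at the last draw; complete data; groups as randomized.

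For one patient's fitted line:
- slope variance: τ² + 1.578(1 − rho)
- intercept variance: rho + 0.449(1 − rho)
- covariance: −0.561(1 − rho)

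With separate group intercepts, the first line is the variance that enters the test. With a common baseline mean it falls by covariance²/intercept variance. Example, rho 0.5 and τ = 0: slope variance 0.789, intercept variance 0.725, covariance −0.280. The reduction is 0.0786/0.725 = 0.108, which leaves 0.681, a ratio of 0.863.

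| rho | τ | variance ratio | power as planned | power, common baseline mean |
|---|---|---|---|---|
| 0.3 | 0 | 0.77 | 76.0% | 84.8% |
| 0.3 | 0.5 | 0.81 | 68.4% | 76.0% |
| 0.3 | 1 | 0.88 | 52.4% | 56.8% |
| 0.5 | 0 | 0.86 | 87.2% | 91.2% |
| 0.5 | 0.5 | 0.90 | 78.2% | 82.0% |
| 0.5 | 1 | 0.94 | 58.1% | 60.3% |
| 0.7 | 0 | 0.93 | 97.4% | 98.1% |
| 0.7 | 0.5 | 0.95 | 89.6% | 90.8% |
| 0.7 | 1 | 0.98 | 65.2% | 66.1% |

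At rho 0.8 the gain is below half a point for each of these τ.

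**4. Sensitivity.** With τ = 0.5 and an intercept–slope correlation of −0.3, the cut runs from 27% at rho 0.3 to 12% at rho 0.8. With +0.3 it runs from 12% to about zero. Draws at 0, 2, 8 and 20 h make it slightly larger (ratio 0.844 instead of 0.863 at rho 0.5, τ = 0).

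**5. The expected power gain.** The planned slope test beats the plain two-sample calculation only if τ² + 1.578(1 − rho) < 1. That needs rho above about 0.37 when τ = 0 and above about 0.52 when τ = 0.5. It cannot happen when τ = 1.

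**6. Degrees of freedom.** With four response times, discrete treatment-by-time has 3 d.f. Two d.f. fit baseline plus two later draws, or three post-transfusion draws with baseline as a covariate.

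**The case against.** A random intercept and slope model with a treatment-by-time test is a standard, valid analysis, and it matches an outcome defined as change. A reader might infer bias, or that a chance baseline imbalance produces a spurious opposite trend. The documents support neither: with groups as randomized, the change and baseline-adjusted contrasts target the same effect, and chance imbalance is ordinary sampling error already reflected in the standard error.

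A reader might also infer that the 78 is wrong, or that the interaction test sized the trial. It did not. The 78 is a correct two-sample calculation; only the aim is shared.

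It is tempting to quote the 16- and 9-point gains as the loss in the primary analysis, or to apply the rule that change is worse than ignoring baseline below rho 0.5. Both belong to a single pre–post pair. For the primary slope test the gains are smaller and the break-even rho depends on the random-slope variance.

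Finally, the plan is silent on adjustment; it does not exclude it. The model is only the one considered first, and the 2 d.f. test would fit baseline as a covariate. Listing baseline among the time points favours the reading taken here but does not settle it.

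All of this stands as a limit on scope. It does not remove the precision gain at low to moderate correlation or the unsupported power statement.

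**Conclusion.** The point holds as one of efficiency and specification, with no invalidity and no sample size error. For the planned slope test, a common baseline mean removes about 12–23% of the variance at rho 0.3, 6–14% at 0.5 and 2–7% at 0.7. At 77 per arm that is about 4–9, 2–4 and 1 power points, and it is negligible at rho 0.8 or above. These ranges rest on the assumed draw times, uncorrelated random effects, τ from 0 to 1 and an effect of 0.4 SD at the last draw. The documents supply no rho, so no single figure can be claimed.

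The plan's expectation of higher power is not assured: at rho 0.3 the slope test has 76% even without random-slope variance, and at rho 0.5 with τ = 0.5 it has 78%.

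The figures also presume randomized groups. The planned regrouping by cells received means that randomization no longer guarantees equal baseline means. In those groups, change and covariate-adjusted estimates can differ in what they estimate as well as in precision.

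**What to change.** In Statistical Considerations, Aim 2:
- Model the three post-transfusion draws, with the patient's own baseline biomarker and its interaction with time as covariates.
- Test the treatment effect at those draws, or averaged over them. A slope among post-transfusion draws alone would miss a change already present at the first one.
- The covariate model does not require equal baseline means, so it can also be used although the baseline draw follows the transfusion decision. If the constrained model with a common baseline mean is preferred, use it only with patients grouped as randomized.
- State that in the regrouped analysis change and covariate-adjusted estimates can differ.
- Reconcile the number of time points and the 2 d.f. test with the four listed draws.
- Use baseline-adjusted values in O'Brien's global test.

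In Sample Size Considerations, replace the sentence on repeated measures with the power of the chosen test over a stated range of rho.

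Cost: wording only, with no added samples or patients. Patients without a baseline draw need imputation in the covariate version; the constrained model can keep them.

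### Aim 2a: 78 per group fits one unadjusted test at the median effect, but the plan runs a corrected group-by-time test on each of four or seven biomarkers and states no power for it

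*Combined protocol and SAP*

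**What the plan says.** Sample Size Considerations sizes the trial on the Aim 2a mechanistic outcomes. It takes 0.4 SD, the median over a range of biomarker effect sizes, with equal allocation and two-sided alpha 0.10, and concludes that "the sample size for this study is estimated to be $n=78/group". It points the alpha to a later paragraph ("see additional statistical considerations below") and adds: "Actual power is expected to be higher on account of the repeated measures design". No target power is given for Aim 2a.

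The Aim 2 paragraph of Statistical Considerations describes the analysis. The starting form is a mixed model: "A model with a random slope and intercept will be considered initially". The quantity to be tested is then named: "the primary parameter of interest will be the treatment group by time interaction". The model is fitted separately to each biomarker. Multiplicity is handled by a cited method whose title in the reference list describes it as Bonferroni-based and meant for correlated endpoints. O'Brien's nonparametric global statistic is computed in addition.

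The panel differs by section. Aim 2a in Specific Aims and Table 5 each list seven markers (IL-6, IL-8, vWF, ICAM-1, RAGE, SP-D, PAI-1). The preliminary-data section on biomarkers as intermediate outcomes says the panel was refined to IL-6, IL-8, PAI-1 and RAGE for Aims 2a/c. The assay text under Specimen Handling and Laboratory Assays names those four for Aim 2a.

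The recruitment target is meant to cover drop-out and patients in whom washing proves not feasible: "we plan to enroll and randomize patients until 154 patients have undergone surgery and had at least one transfusion on the operative day". More than that must be randomised to reach it: "We anticipate this may require randomizing up to 190 total patients". Those already in the pipeline are kept: "Any patients randomized and awaiting surgery when the 154th patient is achieved will also be included". The section closes by allowing the final size to be adjusted after the two-stage feasibility results.

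**The concern.** The calculation and the analysis describe different tests. A sample size for one comparison at 0.10 does not show what the trial can detect when each of several markers is tested at a smaller, corrected level on a different parameter, the slope difference. The correction cannot be pinned down while the panel is both four and seven. If the panel stays open until results are known, so does the threshold each marker must pass. The one sentence that speaks to power claims a gain from repeated measures, but gives no within-patient correlation, slope variance or corrected alpha to support it.

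At stake is how a negative result for a single biomarker is read. If power for that marker was 50-60%, a null result says little; if it was about 90%, it says a good deal. The plan does not let a reader tell which applies. A smaller matter is that the target described as allowing for losses lies below the calculated requirement.

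**Working it through.** **Inputs from the documents.** Effect 0.4 SD, two-sided alpha 0.10, 1:1 allocation, 78 per group, 154 transfused patients (77 per arm), four or seven markers. **Assumed, because not stated:** 80% target power; 0.10 as the family-wise level; the correlations and variances named below.

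**1. The plan's figure.** n = 2(1.645 + 0.842)² / 0.4² = 77.3, so 78 per group. Exact noncentral t power at 78 is 80.0%. Alternatives do not fit: two-sided 0.05 at 80% needs 99, one-sided 0.10 at 80% needs 57, and two-sided 0.10 at 90% needs 108. So 78 is the size for one unadjusted two-sample test at 80%.

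**2. Same single-measurement test, corrected, 77 per arm.** The noncentrality is 0.4/√(2/77) = 2.482.
- Alpha 0.10: 79.6%.
- Alpha 0.10/4 = 0.025: 58.7%; effect detectable with 80% power 0.50 SD.
- Alpha 0.10/7 = 0.0143: 50.3%; detectable effect 0.54 SD.

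Plain Bonferroni is the lower bound, since the cited method allows for correlated endpoints. With an assumed common between-marker correlation of 0.3 to 0.7, power is 60-65% (four) or 52-59% (seven).

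**3. Group-by-time slope test, 77 per arm.** Assume linear divergence reaching 0.4 SD at the last draw, compound symmetry with within-patient correlation r, no random slope, and draws at about 0, 1, 7 and 19 h. The mean time is 6.75 h and the sum of squares about it is 228.75. On the scale of the last-draw difference, the per-patient variance is (1 − r) x 19²/228.75 = 1.578(1 − r). The noncentrality is 0.4/√(2 x 1.578(1 − r)/77), which is 2.36, 2.79 and 3.61 for r = 0.3, 0.5 and 0.7.

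| r | alpha 0.10 | 0.10/4 | 0.10/7 |
|---|---|---|---|
| 0.3 | 76% | 55% | 46.5% |
| 0.5 | 87% | 71% | 63.5% |
| 0.7 | 97.5% | 91% | 88% |

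Power reaches 80% at r of about 0.37, 0.59 and 0.64 respectively.

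**4. Sensitivity at r = 0.5.** If the planned random slope adds 10% or 20% of baseline variance at the last draw, the variance rises from 0.789 to 0.889 or 0.989. Power becomes 84% or 80% unadjusted, 65% or 60% (four), and 57% or 52% (seven). With three draws (0, 7, 19 h) and no random slope it is 81%, 61% and 52%.

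**5. O'Brien's global test.** If all k markers have a 0.4 SD effect and common correlation ρ, the normal-theory effect on the summed score is 0.4√(k/(1 + (k − 1)ρ)). At ρ = 0.3, 0.5 and 0.7, 77 per arm and alpha 0.10, power is 97%, 93% and 88% for four markers, and 99%, 95% and 89% for seven.

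**6. Recruitment target.** 2 x 78 = 156 against 154 costs 80.0% − 79.6% = 0.4 points on the single test. Assumed specimen losses of 5% or 10% from 154 leave about 73 or 69 per arm, giving 77.7% or 75.6%.

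**The case against.** The best defence is that 78 is correctly computed, that this is an early-phase trial which openly relaxes alpha and leaves clinical efficacy to later work, and that repeated measures may more than repay the correction. All of that stands. Step 3 shows it happening once within-patient correlation passes about 0.6, absent a random slope. O'Brien's test also gives the panel one comparison that needs no per-marker correction. It is supplementary, however: the named primary parameter is the interaction, modelled marker by marker, and no power is stated for the global test either.

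The figures above need care as well. The 0.4 SD is a median, so they describe a marker at that effect and not each marker. On a single measurement, 0.5 SD gives 80% (four) or 73% (seven), and 0.3 SD gives 35% or 27%. Equal arms are assumed, although the modified intention-to-treat rule moves washing-arm patients given no washed unit into the control group. The effect is small: 69 against 85 patients gives 79.2% on the unadjusted test. The mention of three time points, where four draws are listed, may mean changes from baseline at three later draws.

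A reader might infer that the trial is underpowered, or that the repeated-measures sentence is false. The documents support neither, because the quantities that decide it are absent. Nor is 154 against 156 a material shortfall: patients awaiting surgery, or the permitted further adjustment, may close it. Equally, 190 should not be read as a margin on 154, because randomisation stops at the 154th transfused patient; the 190 replaces patients who never reach transfusion.

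**Conclusion.** The concern holds as a mismatch between the sizing basis and the planned test, together with a contradictory panel. It does not hold as an arithmetic error in 78. For a marker at the median effect, with 77 per arm and 0.10 assumed family-wise, corrected power is at least 58.7% (four) or 50.3% (seven) on a single measurement. For the slope test it is 55-91% or 47-88% over within-patient correlations of 0.3 to 0.7, under compound symmetry with four draws and no random slope; adding one lowers these. The claim of higher actual power is thus unsupported for the corrected test. The weakness is confined to conclusions about individual biomarkers, given about 88-99% for the global test if every marker had the 0.4 SD effect. The recruitment target is secondary: the two-patient gap is trivial, but 154 carries no stated margin for the missing specimens that Additional statistical considerations foresees.

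**What to change.** 1. Use one Aim 2a panel in the aims, Table 5, the assay section and the multiplicity correction, fixed before unblinded biomarker results are seen.
2. State whether 0.10 is the family-wise level for that panel, and align this with Additional statistical considerations, which only concedes that family-wise error may rise.
3. Say that 78 per group corresponds to one unadjusted test at the median effect, and state the target power. Restate per-biomarker power and detectable effect for the corrected group-by-time test over a stated range of within-patient and between-marker correlations, naming the number of draws and whether a random slope is included. Give the power of O'Brien's test alongside. Otherwise delete the sentence "Actual power is expected to be higher on account of the repeated measures design".
4. Reconcile 154 with 156, state which losses the allowance covers (before transfusion, non-feasible cases, missing specimens), and give the power at the expected evaluable number.

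The cost is wording and one power calculation. No patients are added and the planned tests do not change. The downside is that the stated per-biomarker power may look less favourable.
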